COMIRB Protocol

COLORADO MULTIPLE INSTITUTIONAL REVIEW BOARD
[name] [contact] [contact]

Protocol #: 20-1866

Project Title: Understanding Affective Processing of Scientific Evidence to Promote Informed Choice for Breast Cancer Screening

Principal Investigator: [name]

Version Date: 5.10.2021

I. Hypotheses and Specific Aims:

Cancer screening for the right patients at the right level of cancer risk can save lives. However, over the last several years most expert groups have de-intensified many screening recommendations as a result of emerging evidence of net harms for certain populations. Newer recommendations for mammography screening highlight a tailored approach based on age and risk and comorbidities, aiming to minimize harms and target women who could benefit the most.¹ Although there is still widespread disagreement about when and how frequently certain populations of women should receive breast screening, one point of agreement is that women should make an informed choice with their doctor about when to start, when to stop, and how frequently to screen.²⁻⁴

However, the change in emphasis from uniformly promoting mammography to promoting informed choice constitutes a medical reversal in the sense that this new message is very different from past messages and people's expectations.^{1,5-7} The result is a delicate situation in which there is need to convey the evidence to women, but also a need to do it in a way that maintains credibility and trust despite this reversal. Research suggests that many women react negatively to mammography evidence, responding with **Reactance** (e.g., "this is trying to manipulate me", "this is trying to ration healthcare"), **self-Exemption** (e.g., "this doesn't apply to me"), **Disbelief** (e.g., "you can't believe all the research"), or **Source derogation** (e.g., "I don't trust this source"),^{6,8,9} which we refer to together as **REDS**. These responses reflect different ways of rejecting of the evidence, stand in the way of informed choice, and could lead to distrust in future screening health messages.

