Altogether, the weight of the evidence suggests that communicating mammography screening evidence can elicit negative reactions. The types of negative reactions that we are particularly concerned about include **Reactance** (i.e. perceived manipulation or influence, e.g. "this is trying to ration healthcare"), **self-Exemption** (e.g., "this doesn't apply to me"), **Disbelief** (e.g., "you can't believe all the research anyway"), and **Source derogation** (e.g., "I don't trust this source"), which we shorten to **REDS**.^{8,9} These responses are sometimes referred to collectively as "defensive coping",³⁶ although we prefer "REDS" to refer directly to the four types of responses. To date, no research has examined REDS systematically to assess their prevalence and causes in the context of communicating mammography screening evidence. And even though many women

react negatively to screening information, many women also want to be informed and be able to make a choice.³⁷ The result is a delicate situation in which there is need to convey the evidence to women, but also a need to do it in a way that maintains credibility and trust.

III. Preliminary Studies/Progress Report:

IV. Research Methods

A. Outcome Measure(s):

The primary outcome measures in this survey are REDS responses and screening intentions. See Table 1 below for all survey measures.^{35,55,56,61,66,72,96-99}

	Measure description	Source
Primary DVs	REDS responses	See appendix
	Screening intentions	Schapira et al. 2019
Secondary DVs	Change in trust in provider and healthcare system, pre vs. post BCS-DA	Egede et al. 2008
	Positive responses, e.g. appreciation of information	Ad hoc
	Change in screening knowledge, pre vs. post BCS-DA	Schapira et al. 2019
IVs: primary	Breast cancer risk perceptions: affective, deliberative, experiential	Ferrer et al. 2016
	Perception of net screening benefit (benefits minus harms) at pre-test	[name] et al., 2018
	Objective breast cancer risk	Schapira et al. 2019
	Cognitive responses to information	See appendix
	Medical Maximizing-Minimizing orientation	[name] et al., 2016
	Perceived norms	Hersch et al., 2015
	Past screening experience	Petrova et al., 2015
Secondary IVs and control variables	Perceived barriers to screening	Hyman & Baker 1992
	Friends/family experience with breast cancer	Petrova et al., 2015
	Subjective numeracy	Fagerlin et al., 2007
	Health literacy	Chew et al., 2008
	Demographics	Standard questions

Table 1. Aim 1 measures.

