B. Description of Population to be Enrolled:

Inclusion:

- Female
- Between 39-49 years of age
- No history of breast cancer
- No known BRCA1/2 mutation

Exclusion:

- Non-English or Spanish Speaking
- Persons unable to provide informed consent (e.g. severe dementia or cognitive disability or illiterate)
- History of breast cancer
- Known BRCA1/2 mutation

Pilot Survey: We will pilot test questions to measure REDS and cognitive reactions to assess item variability, internal consistency, and reduce the total number of items. We will recruit 700 women through Dynata. Dynata manages an online participant panel of millions of adults across the United States. Participants who are part of Dynata's panel have agreed to participate in surveys in exchange entry into lotteries for small cash prizes.

Pilot Interviews: We will recruit up to 15 women from [name]'s Internal Medicine clinic at UCHealth. These interviews will focus on assessing overall knowledge and understanding of the information presented in the decision aid. Participants will receive a \$25 gift card for participating in the interview.

Nationally Representative Survey: We will recruit 700 women age 40-49 through Ipsos Public Affairs. Ipsos manages an online participant panel allowing population inferences using probability sampling methods and providing Internet access to households that do not have it.

Nationally Representative Interviews: We will recruit up to 40 women from the Ipsos survey who agreed to be contact for a follow-up phone interview. We will specifically recruit women who expressed negative reactions to mammography evidence, so that we can assess how to improve the BCS-DA using insights from those who were negatively affected. We will attempt to recruit at least 25% non-White participants for these interviews.

C. Study Design and Research Methods

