## Variables

Manipulated variables

Not applicable (observational study)

*No files selected*

Measured variables

Reaction to screening benefits: Reactance (4 items), Self-exemption (4 items), Disbelief (4 items)

Reactions to overdiagnosis: Reactance (4 items), Self-exemption (4 items), Disbelief (4 items)

Reactions to false positives: Reactance (4 items), Self-exemption (4 items), Disbelief (4 items)

Bayesian updating (4 items) – asked three times for the three domains (benefits, overdiagnosis, false positives) Source trust/derogation in reaction to DA as a whole – 4 items Each of the items indicated above are Likert scale questions Screening intentions: categorical outcome (screen before 50, wait to screen until 50, never intend to screen) Screening knowledge (Hersch et al 2015) – add up number of questions or proportion correct (pre-DA and post-DA)

*No files selected*

Indices

We will compute Cronbach's alpha reliability for the REDS items to justify collapsing them into a single measure (mean of all items). We will compute correlations among the REDS scores (10 scores: source derogation to decision aid (DA) as a whole; reactance, self-exemption, and disbelief for benefit, overdiagnosis, false-positives). If responses across the three domains are highly correlated ( $r>0.50$ ), and the Cronbach's alpha among the individual items is also high

(alpha>0.70) then we will further reduce the data by collapsing across the domains to obtain a mean score. This would result in a single score for each REDS construct (4 total scores). Otherwise, if responses are moderately correlated we will use multivariate analyses to test hypotheses, and if responses has low correlation we will test hypotheses below separately for reactions to benefits, overdiagnosis, and false-positives.

*No files selected*

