## Analysis Plan

Statistical models

H1. Perceived discordance with prior knowledge will predict REDS. • Dependent variable: Overall score averaged across REDS domains [Continuous] • Independent variable: Bayesian updating (4 items) averaged [Continuous] • Hypothesis: Higher (more negative) scores on conflicts with prior knowledge (Bayesian updating) will be correlated with higher (more negative) scores for other domains • Hypothesis: Higher correlation for the benefits domain than the other two domains (overdiagnosis and false positives) • Analysis: Compute bivariate correlation between these two scores within each informational domain; No plans to adjust for covariates in this analysis. Fit linear regression model (correlation) for association between Bayesian updating and REDS. H2. Perceived threat and screening efficacy will predict REDS • Dependent variable: Overall REDS [Continuous] • Independent variable: Pre-test perceived threat (average of 3 affective risk questions; should have high reliability) [Continuous] • Independent variable: Pre-test screening efficacy (questions on how beneficial and harmful is screening) = (perceived benefit – perceived harm) [Continuous] • Hypothesis: Women who perceive high affective cancer risk AND have high preexisting expectations for screening will express strongest (most negative) REDS • Analysis: Linear regression model for overall REDS with interaction term between perceived threat and efficacy (interaction effect indicates that the effect of perceived threat on REDS is modified by screening efficacy) • Interpretation/Visualization: Will make at least one of the variables binary H3. Perceived threat and screening efficacy will predict information rejection after controlling for discordance with prior knowledge (Bayesian updating). • Dependent variable: Overall REDS [Continuous] • Independent variable: Perceived threat (average of 3 affective risk questions) [Continuous] • Independent variable: Screening efficacy (perceived benefit – perceived harm) [Continuous] • Independent variable: Bayesian updating (4 item) [Continuous] • Hypothesis: Contribution of Bayesian updating will be less than the emotional factors • Analysis: In regression model for H2, adjust for Bayesian updating and assess interaction effect and effect of Bayesian updating. Compare to models H1 and H2 and assess whether fit (total variance explained; R-squared) is improved (change in variance when you add the second set of predictors). Perform analysis for each of the domains and see if results are consistent across the domains. SH1: Other significant predictors of REDS • Predictors: 1. stronger injunctive norms (i.e. people think I should screen), 2. Medical maximizing (vs. minimizing), 3. Prior screening use (yes/no), 4. Have friends or family diagnosed with breast cancer (vs. not), 5. Lower pre-test trust in the healthcare system, 6. Viewing screening as a protected value (i.e. moral imperative), 7. Structural barriers, 8. Pre-test knowledge • Analysis: Perform bivariate analyses to assess for the association between the predictors and the REDS. We will also add these variables to the H3 models, to test the unique

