#### *No files selected*

#### Transformations

The REDS components and Bayesian updating scores will be computed by averaging across the Likert scale questions. The overall REDS score will be averaged across the REDS domains. Additional averaging across the settings of screening benefits, overdiagnosis, and false positives will be performed if there is strong correlation. Perceived threat will be an average of the three affective risk questions. Pre-test screening efficacy will be computed as (Perceived benefit - Perceived harm).

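### No model of REDS includes objective breast cancer risk, so part of the link between affective threat and REDS could reflect actual risk acting through self-exemption

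*SAP*

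**What the plan says.** **Outcome.** Protocol Section I says of the four REDS reactions: "These responses reflect different ways of rejecting of the evidence, stand in the way of informed choice". Self-exemption is one of the four, and nothing in its definition or scoring depends on the woman's own risk. The SAP (Measured variables) gives it four items in each of three information domains, for example "Reactions to overdiagnosis: Reactance (4 items), Self-exemption (4 items), Disbelief (4 items"). Under Transformations, "The overall REDS score will be averaged across the REDS domains", with higher scores read as more negative.

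**Population.** Protocol Section IV.B limits risk at entry only by excluding a history of breast cancer or a "known BRCA1/2 mutation". There is no upper limit on calculated risk, and H4 relies on higher-risk women being in the sample.

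**Objective risk.** Protocol Table 1 lists "Objective breast cancer risk" among the primary independent variables. In Section IV.C each woman learns her estimate before she reports risk perceptions and before she reacts to the evidence.

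**Models.** H1 relates REDS to discordance with prior knowledge. H2 is the "Linear regression model for overall REDS with interaction term between perceived threat and efficacy". H3 adds discordance to H2, compares R-squared across models, and treats threat and efficacy as the emotional predictors. SH1 and SH3 add norms, maximizing, prior screening, friends or family with breast cancer, trust, protected value, structural barriers, pre-test knowledge and insurance. Objective risk enters only H4 and H4a, where the outcome is screening intention.

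**The concern.** A woman who has just been told that her risk is well above average may say that general evidence does not fit her, and she may be right. The score records this as rejection. The same woman is likely to report higher affective threat. Objective risk then lies upstream of both the predictor and one part of the outcome, and the H2 and H3 models cannot account for it.

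The SAP itself accepts that self-exemption can have a reasoned basis: SH2 explains it among Black women by their under-representation in clinical trials. It does not extend that reasoning to risk.

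At stake is the interpretation of the threat coefficient and of the H3 comparison of variance explained. Both are meant to show emotional predictors outweighing a cognitive one. If actual risk contributes to the threat association, the emotional label claims more than the model can show.

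**Working it through.** **1. The plan's own figure.** The SAP (Sample size rationale) states that 500 women give 80% power for a 1.2% increment in R-squared when other factors explain 20%, alpha 0.05.
- f² = 0.012 / (1 − 0.20 − 0.012) = 0.01523
- λ = 500 × 0.01523 = 7.61
- Power from the noncentral F with 1 df = 0.786. The increment for exactly 80% is 1.24%, so the stated figure reproduces.

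**2. Weight of self-exemption in the score.** It has 3 × 4 = 12 items. REDS has 3 × 12 + 4 = 40 items, counting the four on source derogation. The weight is 12/40 = 30% if items are averaged, or 1/4 = 25% if four construct scores are averaged.

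**3. Dilution.** Assume unit-variance constructs correlated at 0.5, with risk acting only on self-exemption (correlation s).
- Construct weights: SD of the mean = √(4 + 12 × 0.5)/4 = 0.791, so corr(risk, REDS) = (0.25/0.791)s = 0.316s.
- Item weights (0.3, 0.3, 0.3, 0.1): variance = 0.28 + 0.36 = 0.64, SD = 0.8, so corr(risk, REDS) = (0.3/0.8)s = 0.375s.

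**4. False-positive rate for threat.** Let a be the risk–threat correlation and let threat have no effect of its own. The induced threat–REDS correlation is r = a × 0.316s or a × 0.375s. Then z = atanh(r) × √497, and the rejection probability is Φ(z − 1.96) + Φ(−z − 1.96). The documents give no value for a, s or the correlation between constructs; all are assumptions. N = 500 is the SAP figure.

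| a | s | Formula, construct / item weights | Simulation, construct / item weights |
|---|---|---|---|
| 0.2 | 0.2 | 6% / 6% | 5% / 6% |
| 0.3 | 0.1 | 6% / 6% | not run |
| 0.3 | 0.3 | 10% / 12% | 10% / 13% |
| 0.4 | 0.3 | 14% / 17% | 14% / 16% |
| 0.4 | 0.4 | 20% / 27% | 22% / 27% |
| 0.5 | 0.4 | 29% / 39% | 30% / 41% |

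Worked example, last row with item weights: r = 0.5 × 0.375 × 0.4 = 0.075, z = 1.675, probability 0.39. The simulation used 1,500 data sets per setting and right-skewed risk. Adding objective risk to the model returned the rate to about 4 to 6%.

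**5. The threat-by-efficacy term.** In the same simulation its false-positive rate stayed at about 4 to 7% when risk acted additively. It rose to about 6 to 20% when risk affected self-exemption more strongly in women with high screening expectations. Adjusting for risk alone did not correct that (6 to 20%); adding risk by efficacy did (about 4 to 6%).

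**6. Price of adjusting.** If threat has a real 1.2% increment, its unique part is 0.012 × (1 − a²).

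| a | Unique increment | Power |
|---|---|---|
| 0.2 | 1.15% | 0.77 |
| 0.3 | 1.09% | 0.75 |
| 0.4 | 1.01% | 0.71 |
| 0.5 | 0.90% | 0.66 |

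**The case against.** **The premise rests on material not in view.** The REDS item wording is in an appendix, and the documents do not say whether the benefit and harm figures are tailored to each woman's risk. If they are, self-exemption is harder to justify and the concern shrinks. Direction is also uncertain: low-risk women could say that the benefits do not apply to them, which would weaken the correlation. This stands, and the conclusion is conditional on it.

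**The hypotheses are predictive and the survey is cross-sectional.** If risk acts on REDS only through threat, the unadjusted coefficient is not spurious; confounding needs a direct path from risk to REDS. That is correct. But H3 gives the predictors an emotional reading, and the adjusted model is the way to examine it. Risk is upstream of threat, so this is not adjustment for a mediator. That holds whether threat is measured pre-test (SAP) or after risk disclosure (protocol Section IV.C), two descriptions that should be reconciled.

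**SH1 already includes friends or family with breast cancer.** This is a partial proxy. It is yes/no, mixes friends with relatives, and lies outside the H2 and H3 models.

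**Stronger readings that a reader might infer.**
- *The study cannot tell defensive from accurate self-exemption.* The documents do not support this: component scores and objective risk are both collected. The separation is possible but not pre-specified.
- *The H2 interaction test is undermined.* It is not, unless risk also interacts with screening expectations, which is a further assumption.
- *False positives could reach 61 or 92%.* Those values follow from a = 0.5 and a correlation of risk with overall REDS of 0.2 or 0.3 (r = 0.10 or 0.15). Through self-exemption alone, 0.2 needs s = 0.2/0.375 = 0.53 to 0.2/0.316 = 0.63, and 0.3 needs s = 0.80 to 0.95. These are implausibly high.

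**Conclusion.** The point holds in a limited form. It is certain from the documents that self-exemption always counts as rejection, that objective risk is a primary independent variable disclosed before reactions, and that no REDS model contains it. It is conditional that this distorts the results. That requires evidence not fully tailored to risk and a direct association of risk with self-exemption.

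The exposure is mainly the threat main effect and, through it, the H3 R-squared comparison. Under the assumptions shown, the false-positive rate for threat is about 6 to 40% instead of 5%, and near the nominal level if the correlations are weak. This is a gap in pre-specification that is cheap to close, not a defect that invalidates H2 or H3.

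**What to change.** Amend the SAP before analysis:

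1. Pre-specify H2, H3 and the SH1 multivariable model both without and with objective risk (continuous).
2. For the interaction test, also add risk by efficacy to the adjusted model.
3. Repeat H2 and H3 with REDS computed without self-exemption, and with self-exemption as a separate outcome.
4. State that a threat association will be described as emotional only in light of the risk-adjusted result.
5. State whether the evidence shown is tailored to individual risk, and reconcile the timing of the threat measure between the two documents.

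No new data are needed. The cost is one or two degrees of freedom, an extra table, and some loss of power for threat in the adjusted model: for a 1.2% increment, from about 0.79 to between 0.66 and 0.77 if risk and threat correlate at 0.2 to 0.5. Reporting both versions shows the reader how much the adjustment matters.

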The length of the survey may be an issue since we are recruiting through Ipsos.

There is a possibility that not a sufficient amount of subjects with voluntarily self-identify for the follow-up interviews.

F. Data Analysis Plan:

Pilot Survey: We will check the variability of each questionnaire item to assess suitability for exploratory factor analysis. Exploratory factor analysis will be used to identify the factor structure of the REDS items. Items that do not load onto any factor will be dropped. Reliability of the remaining items

Nationally Representative Survey: Summary statistics will estimate the prevalence of REDS to each part of the BCS-DA. Simple within-subjects tests (e.g. ANOVA) will compare REDS in response to screening benefits, false positives, and overdiagnosis.

All Interviews: We will conduct exploratory content analysis of these qualitative interviews using the analytic program Dedoose to extract themes in patients' reactions to the presented information.

Safety Oversight:

The principal investigator will be responsible for the conduct of this study, overseeing participant safety, executing the data and safety monitoring (DSM) plan, and complying with all reporting requirements to local and federal authorities. This oversight will be accomplished through additional oversight from the Data and Safety Monitoring Committee (DSMC) at the University of Colorado Cancer Center (CU Cancer Center). The DSMC is responsible for ensuring data quality and study participant safety for all trials at the CU Cancer Center. A summary of the DSMC's relevant activities is as follows:

- Conduct of internal audits

- Has the authority to suspend studies for safety or conduct issues
- May submit recommendations for corrective actions to the CU Cancer Center's Executive Committee

Study audits conducted by the DSMC will consist of a review of the regulatory documents, consent forms, and source data verification. Documentation of the audit conducted by the DSMC will then need to be submitted to the IRB of record at the time of the IRB's continuing review of this trial (if applicable).

G. Summarize Knowledge to be Gained:

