## Study Information

### Hypotheses

**SPECIFIC AIM 1: Predictors of REDS PRIMARY HYPOTHESES:** H1: Perceived discordance with prior knowledge will predict REDS. We developed an assessment of the degree to which the DA information conflicts with prior knowledge. We predict that when the DA information conflicts with an individuals' prior knowledge about BCS, they will express more disbelief, reactance, self-exemption, and source derogation. H2: Perceived threat and screening efficacy will predict REDS. We derive our predictions from the Extended Parallel Process Model (EPPM) which is an extension of the fear appeal model. The EPPM proposes that people are most likely to reject information when they feel threatened AND feel they cannot do anything to address the threat (i.e. a high threat, low efficacy message). We predict that women who perceive high affective cancer risk AND have high preexisting expectations for screening will express the strongest reactance, self-exemption, disbelief and source derogation (because they experience the DA as a high threat, low efficacy message). We will test this hypothesis by examining pre-test screening expectations (perceived screening benefit minus perceived harm), and pre-test affective cancer risk perceptions, as predictors of "REDS" outcomes. H3: Perceived threat and screening efficacy will predict information rejection after controlling for discordance with prior knowledge. Putting predictors from H1 and H2 together in a model, discordance with prior knowledge will no longer be a significant predictor of REDS whereas affective cancer risk and preexisting expectations of screening will continue to be significant predictors. **SECONDARY HYPOTHESES:** SH1: Other significant predictors of REDS responses will include: 1. stronger injunctive norms (i.e. people think I should screen), 2. Medical maximizing (vs. minimizing), 3. Prior screening use (yes/no), 4. Have friends or family diagnosed with breast cancer (vs. not), 5. Lower pre-test trust in the healthcare system, 6. Viewing screening as a protected value (i.e. moral imperative). We predict that all of these variables will show significant bivariate correlations with REDS responses but we do not have specific hypotheses about which will be significant in a model including all predictors. SH2: Relative to White women, Black women will express more self-exemption (feeling that the information does not apply to them) but not necessarily more disbelief, reactance or source derogation. Our rationale for using race as a predictor is that, due to longstanding health disparities related to insufficient care among minority women, and a historic lack of inclusion of BIPOC individuals in clinical trials, Black women will be more likely than White women to believe that the information does not apply to them. SH3: Factors that will not significantly predict REDS will include: 1. Insurance status, 2. Structural barriers, 3. Pre-test knowledge. **SPECIFIC AIM 2: Predictors of screening intentions** H4: There will be an association between objective cancer risk and screening intentions such that women at higher cancer risk will be more likely to intend to screen before 50 (vs. wait to screen or not screen at all). H4a: There will also be an interaction such that women with lower REDS responses will show a stronger correlation between objective cancer risk and screening intentions, and women with higher REDS will show smaller or null correlations between objective risk and intentions. H5: There will be an association between post-DA knowledge and

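### Two comparative sub-predictions, under H1 and H3, have no test of the difference, and H3's prediction about discordance is worded in two ways that can give opposite verdicts

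*SAP*

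**What the plan says.** **H3.** The SAP gives the same headline in Hypotheses and in Analysis Plan: "Perceived threat and screening efficacy will predict information rejection after controlling for discordance with prior knowledge". The two sections differ on what happens to discordance, which the Analysis Plan calls Bayesian updating.

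- Hypotheses: "discordance with prior knowledge will no longer be a significant predictor of REDS", while affective risk and prior screening expectations stay significant.
- Analysis Plan: "Hypothesis: Contribution of Bayesian updating will be less than the emotional factors".

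The planned analysis takes the H2 model (threat, efficacy and their product), and the instruction is to "adjust for Bayesian updating and assess interaction effect and effect of Bayesian updating". It then compares R-squared with the H1 and H2 models, described as the "change in variance when you add the second set of predictors".

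**H1.** The Analysis Plan adds a prediction that the Hypotheses section does not contain: "Hypothesis: Higher correlation for the benefits domain than the other two domains (overdiagnosis and false positives". The matching analysis is "Compute bivariate correlation between these two scores within each informational domain", plus a regression of REDS on discordance.

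**Elsewhere.** The protocol's Data Analysis Plan says "Simple within-subjects tests (e.g. ANOVA) will compare REDS in response to screening benefits, false positives, and overdiagnosis". The SAP's Inference criteria promise a multiplicity adjustment when one hypothesis is tested in several domains. The SAP's Indices section averages across domains if they correlate above 0.50 and alpha exceeds 0.70, and mentions multivariate analyses for moderate correlation without naming a contrast.

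**The concern.** Both sub-predictions say that one association is larger than another. Testing each association against zero does not answer that.

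For H3, under the Hypotheses wording a missed discordance effect counts as support. Under the Analysis Plan wording, two estimates would be compared by eye. The wordings part company when discordance is smaller than the other factors but still significant: the first is then refuted and the second fits. The SAP is registered before analysis, and this leaves the choice of version open until the result is known.

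For H1, a benefits-first ranking could be reported as confirmation when the three correlations do not differ. The protocol's within-subjects comparison does not fill the gap, because it compares REDS levels across domains and not the strength of their association with discordance.

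At stake is the statement, within primary Aim 1 hypotheses, that discordance matters less than threat and efficacy.

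**Working it through.** **1. The plan's own figure.** SAP, Sample size rationale: N = 500, other factors explain 20%, increment 1.2%, 80% power, alpha 0.05 (taken as two-sided). For one added term, f² = 0.012/(1 − 0.212) = 0.01523 and λ = 500 × 0.01523 = 7.61. With F(1, 494), power is 78.6%, which reproduces the stated 80% within 2 points. A real discordance effect of that size is missed in 21% of surveys. At an assumed 0.6%, f² = 0.006/0.794 = 0.00756, λ = 3.78, and the miss rate is 51%.

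**2. H3, equal true slopes.** The documents give no correlations, so these are assumptions. Threat (T), efficacy (E) and discordance (D) are standardised with pairwise correlation ρ = 0.1, 0.3 or 0.5. Each has the same marginal correlation r with REDS, so each slope is r/(1 + 2ρ). The fitted model is T + E + T×E + D at N = 500. The pattern counted is the full Hypotheses one: D significant alone, D non-significant jointly, T and E both significant.

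| r | Pattern appears (range over ρ) |
|---|---|
| 0.10 | about 1–4% |
| 0.20 | about 3–17% |
| 0.25 | 0% to about 19–20% |
| 0.30 | 0–15% |
| 0.40 | 0–2% |
| 0.50 | 0% |

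Requiring D to be significant alone matters only for weak associations. Without it, the r = 0.10 row would read 1–12%.

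**3. H3, discordance slope half the others'.** The Analysis Plan prediction is now true, read as slopes. D remains significant, so the Hypotheses version fails, in about:

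- 52–63% of samples at 0.10 v 0.20
- 93–97% of samples at 0.15 v 0.30

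**4. What the R-squared comparison gives.** Combined model minus H1 model is the unique R-squared of the threat/efficacy set. Combined minus H2 is that of discordance. The first sets three terms (two without the product) against one. With equal slopes and r = 0.10–0.30, the set's unique R-squared exceeds discordance's in 79–98% of samples. A larger value for the set therefore does not show that discordance has the smaller slope.

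**5. H1.** With three equal true correlations and the same dependence between domains, symmetry puts benefits first one time in three. For assumed r of 0.1–0.5 and cross-domain correlation of 0.3–0.7, the SD of a difference between two correlations from the same women runs from 0.0336 to 0.0586. With alpha split over two comparisons, the gap detectable with 80% power is SD × (2.241 + 0.842): 0.0336 × 3.083 = 0.10 to 0.0586 × 3.083 = 0.18.

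**6. Precision of an H3 slope comparison.** For T against D, ignoring the centred product term, SE = √[2σ²/(N(1 − ρ))], where σ² is the residual variance. At slopes 0.20/0.20/0.10 and ρ = 0.3:

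- R² = 0.04 + 0.04 + 0.01 + 2(0.3)(0.04 + 0.02 + 0.02) = 0.138, so σ² = 0.862
- SE = √[2(0.862)/350] = 0.070
- the chance that the 95% CI lies above 0 is Φ(0.10/0.0702 − 1.96) = Φ(−0.535) = 30%

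Over ρ = 0.1–0.5 the same formula gives 23–35% at 0.20 v 0.10 and 57–73% at 0.30 v 0.15.

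**The case against.** The strongest reply is that H3 already compares contributions. Comparing the combined model with the H1 and H2 models yields both unique R-squared values on one scale, and because the analysis builds on the H2 model, the emotional factors are most naturally threat, efficacy and their product. This stands in part: the estimates are planned, and what is missing is an interval for their difference and a statement of what counts as less.

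A second reply is that the wordings are a strong and a weak form of one idea. That is fair, and it makes the repair a matter of alignment. The SAP still has to say which form decides, since step 3 shows they can disagree often.

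Third, the H1 prediction is only an Analysis Plan bullet, the design is a non-randomised cross-sectional survey, and every size beyond the 1.2% increment is assumed. All of this stands and limits the severity.

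A reader might go further and infer that H1 or H3 is untested, or that the Hypotheses wording generally yields false support. The documents do not support either inference. The H3 combined model tests its headline, the H1 correlations and regression test its headline, and false support fades to 0–2% at r = 0.40.

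**Conclusion.** The point holds for two sub-predictions only. No test or interval is planned for H1's benefits-first ranking or for H3's claim that discordance contributes less, and H3's two wordings can return opposite verdicts on the same data. Non-significance of discordance would not show that it contributes less.

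False support for H3 under equal slopes is a risk mainly at weak to moderate association, peaking at about 19–20% near r = 0.25 with ρ = 0.5. The conflict between wordings grows as associations strengthen. These figures rest on assumed slopes, normal predictors and a common predictor correlation of 0.1–0.5. The H1 one-in-three figure needs only symmetry. Severity is minor to moderate.

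**What to change.** **H1.** Test the benefits correlation against each of the other two domains, by a dependent-correlation test or a domain-by-discordance interaction in a repeated-measures model, adjusted for two comparisons. State that domain-level scores are kept for this test even if the Indices collapsing rule is met.

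**H3.** Keep the headline test. Use one wording for discordance in Hypotheses and Analysis Plan, and choose one estimand in advance. The natural choice is a per-predictor comparison of standardised coefficients with predictors centred: threat against discordance, and efficacy against discordance. Do not average signed coefficients, since opposite signs would cancel. If the block R-squared difference is preferred, say that it is a claim about the set. Report a 95% CI for the difference and the discordance coefficient with its own CI. State that an interval including 0 is inconclusive, and that non-significance will not be read as no contribution or a smaller one.

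**Cost.** A few sentences and a little extra analysis of variables already planned. The drawback is limited power, so an inconclusive result is likely unless the difference is large. The H3 slope comparisons have the power shown in step 6, and less if adjusted for two comparisons. The H1 test has about 30–69% power per comparison for a gap of 0.10 and 67–98% for 0.15 (base correlation 0.2–0.4 assumed).
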